9.5 MRI-derived Imaging Biomarkers

The exploratory endpoints related to the MRI-derived perfusion and diffusion imaging biomarkers will be analysed by the central imaging laboratory and will be reported separately

9.6 Listings

All observed endpoints will be listed by site, treatment, and subject number. For the laboratory endpoints values outside the reference range (with information on clinically significance) and markedly abnormal values will be flagged.

10 Safety

10.1 General Considerations

Safety parameters will be evaluated for the combined safety analysis data set for all types of lesions combined, for each of the three types of lesions separately, and for endometriosis (endometrioma and DIE), See section 6.3 for the definition of the safety analysis sets. All summaries will be performed by treatment. For adverse events (AE) the following rules will apply:

Treatment period	AE to be included
Pre-treatment period	A pre-treatment adverse event is any adverse event occurring after signed informed consent and before start of IMP or a pre-existing condition that worsens in intensity after signed informed consent but before start of IMP
Treatment emergent AE	A treatment-emergent adverse event is any adverse event occurring after start of IMP and before the follow-up phone call, or a pre-treatment adverse event or pre-existing medical condition that worsens in intensity after start of IMP and before the follow-up phone call.

For safety data where only a partial date has been reported, the following rules will be applied:

- Year and month given: for start dates, starting first day in the month and for stop dates, stopped last day in the month
- Only year given: for start dates, starting 1st of January and for stop dates, stopped 31st of December

10.2 Adverse Events

AEs are classified according to MedDRA version 21.0.

An AE which occurs between signing informed consent and the first dose of the IMP or a pre-existing condition that worsens in intensity after signing of informed consent is defined as a pre-treatment AE. A treatment-emergent adverse event is any adverse event occurring after start of IMP and before the follow-up phone call, or a pre-treatment adverse event or pre-existing medical condition that worsens in intensity after start of IMP and before the follow-up phone call. If the timing of an AE cannot be established in relation to the administration of IMP, it will be considered as a treatment emergent AE. Pre-treatment AEs will be presented in a separate data listing only. AE in connection with screening safety lab values are considered pre-treatment if the blood is sampled prior to treatment.

If causality for an AE is missing then the AE will be considered related. If intensity for an AE is missing then the AE will be considered severe. If seriousness for an AE is missing then the AE will be considered serious. If outcome for an AE is missing then the AE will be considered not recovered.

10.2.1 Overview of Treatment-Emergent Adverse Events

An AE overview summary table will be prepared including the number of subjects reporting an AE, the percentage of subjects (%) with an AE, and the number of events (E) reported, for the following categories:

- All TEAEs
- TEAEs by intensity
- All adverse drug reactions (ADR) (i.e. an AE judged by the investigator and/or sponsor to have a reasonable possible causality to the IMP)
- ADR by intensity
- TEAEs leading to death
- Serious TEAEs
- Serious ADR
- TEAEs leading to discontinuations
- ADR leading to discontinuations

10.2.2 Incidence of Adverse Events

Treatment-emergent adverse events will be summarised.

The tables will display the total number of subjects reporting an AE, the percentage of subjects (%) with an AE, and the number of events (E) reported. AEs will be presented by SOC sorted alphabetically and PT sorted in decreasing frequency of occurrence.

Summary tables will be prepared for:

- All TEAEs
- Mild TEAE
- Moderate TEAE
- Severe TEAE
- All ADR
- Mild ADR
- Moderate ADR
- Severe ADR
- Treatment emergent unrelated adverse events
- TEAEs leading to death

- ADRs leading to death
- Serious TEAE
- Serious ADR
- Non-serious ADR
- TEAEs leading to discontinuation
- ADRs leading to discontinuation
- TEAEs for impulse control disorder search string (see [appendix 2](#))
- ADRs for impulse control disorder search string (see [appendix 2](#))
- TEAEs with an incidence $\geq 5\%$ of subjects in any treatment group
- Non-serious TEAEs with an incidence $\geq 5\%$ of subjects in any treatment group

Supporting data listings will be provided for all adverse events sorted by centre and subject number and date of onset. Further, data listings by MedDRA SOC sorted alphabetically and Preferred Term sorted in decreasing frequency of occurrence will be provided for:

- All TEAE
- Severe TEAE
- Serious TEAE
- TEAE leading to death
- TEAE leading to discontinuation
- Treatment emergent adverse events to be followed up after end-of-trial

10.3 Safety Laboratory Variables

Safety lab values are planned to be measured twice, at baseline (visit 1), at end-of-treatment (visit 8). If multiple blood samples are obtained prior to first dose of IMP the last blood sampling performed prior to the first dose of IMP is used as baseline.

Laboratory variables will be grouped under “Haematology” and “Clinical Chemistry”.

10.3.1 Summary Statistics

Mean change and mean percentage (%) change from baseline at end-of-treatment will be presented for each laboratory variable. In addition, descriptive statistics, i.e., the number of subjects with data, mean (standard deviation), median, minimum, and maximum values, will be presented for both baseline and end-of-treatment as well as for changes from baseline to end-of-treatment (both absolute change and relative change).

10.3.2 Laboratory Variable Changes Relative to Normal Range

Changes relative to normal ranges are presented with shift tables with total number of subjects, and number and percent of subjects who experienced a shift from baseline to end-of-treatment. The laboratory reference ranges are provided by the central laboratory. The following categories for shift tables are defined:

- Low: Values which are below the lower reference range limit;
- Normal: Values which are within the lower and upper reference range;
- High: Values which are above the upper reference range limit.

For all haematology and clinical chemistry variables, shift tables will be prepared to compare baseline values to the end-of-treatment value. More specifically, for haematology and clinical chemistry, tables presenting the changes from *Low* or *Normal* to *High* and from *High* or *Normal* to *Low* will be provided.

10.3.3 Markedly Abnormal Changes

For each laboratory variable, a summary tables will be prepared displaying the number and percentage of subjects in each treatment group with normal baseline values but having at least one pre-specified markedly abnormal value any time after first dose of IMP. Pre-specified markedly abnormal criteria for laboratory tests are given in Appendix 1.

10.3.4 Data Listings

All laboratory values will be listed by subject number and time point. Values outside the reference range (with information on clinically significance) and markedly abnormal values will be flagged.

10.4 Vital Signs

Vital signs (pulse rate, systolic blood pressure, and diastolic blood pressure) are planned to be measured 4 times during the trial, at visit 1, at visit 2 prior to first dose of IMP, at visit 3 and at end-of-treatment (visit 8), for each of the 4 visits vital signs will be measured 4 times; in supine position, in seated position, at 1 minute after standing, and at 3 minutes after standing. For each visit changes in systolic and diastolic blood pressure will be calculated using the minimum standing measurement minus the seated measurement and the minimum standing measurement minus the supine measurement. Baseline for all vital signs analyses will be the values obtained at the last assessment prior to the first dose of IMP.

10.4.1 Summary Statistics

Mean change and mean percentage (%) change from baseline to visit 3 and to end-of-treatment will be presented for each vital signs variable (including change from sitting to standing and from supine

to standing as described above). In addition, descriptive statistics, i.e., the number of subjects with data, mean (standard deviation), median, minimum, and maximum values, will be presented for the observed values (at screening, at baseline, at visit 3, and at end-of-treatment) and for change from baseline (both absolute change and relative change) to visit 3 and at end-of-treatment for each vital signs variable (including change from sitting to standing and from supine to standing as described above).

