4.1.2 Exclusion Criteria

1. Use of depot medroxyprogesterone acetate (MPA) within 10 months prior to the screening visit.
2. Use of gonadotropin-releasing (GnRH) agonists (3-month depot) or dopamine agonists within 6 months prior to the screening visit.
3. Use of GnRH agonists (1-month depot or nasal spray), GnRH antagonists, aromatase inhibitors, danazol, birth control implants (e.g. NEXPLANON), progestogen or levonorgestrel-releasing IUD within 3 months prior to the screening visit.

4. Use of hormonal contraceptives (including combined oral contraceptive pill, transdermal patch, and contraceptive ring) and copper IUDs within 1 menstrual cycle prior to the screening visit.
5. Undiagnosed abnormal vaginal bleeding within the last 3 months of the screening visit.
6. History of recurrent bacterial, fungal or viral vaginal infection (i.e. ≥ 4 episodes within a year).
7. History of malignancy within 5 years prior to the screening visit, except for adequately managed basal cell carcinoma and squamous cell carcinoma of the skin.
8. History of orthostatic hypotension or recurrent syncope.
9. History of mental illness including occurrence of acute psychosis, bipolar disorder and schizophrenia (except for well-controlled mild or moderate anxiety and/or depression with no changes to interventions for 3 months prior to the screening visit).
10. History of sudden sleep onset episodes.
11. Known diagnosis of impulse control disorders including pathological gambling, compulsive buying, hypersexuality, and binge eating.
12. Known positive results of Human Immunodeficiency Virus (HIV) antibody tests.
13. Any other incidental, clinically significant abnormal findings than endometriotic / adenomyotic lesions identified at the screening MRI assessment (e.g. suspected tumour).
14. Any clinically significant abnormal findings from vital signs, blood tests of haematology and clinical chemistry at screening, including alanine aminotransferase (ALT) >2.5 times upper limit of normal (ULN) or bilirubin >1.5 times ULN or creatinine >1.5 times ULN.
15. Any clinically significant abnormal findings at physical examination at screening.
16. Any vaginal or vulvar lesions that would interfere with vaginal ring usage.
17. Current pregnancy as confirmed by a positive serum pregnancy test at screening or planning a pregnancy within the duration of the trial, or currently breast-feeding or less than 6 months post-partum prior to the screening visit.

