7.4.7 Vital Signs

Systolic and diastolic blood pressure as well as pulse will be measured at the screening visit, prior to randomisation at the randomisation visit, within 1-5 days of the first ring insertion (i.e. visit 3) and at end-of-treatment / cycle 4. Vital signs at randomisation will be baseline. Blood pressure and pulse should be measured by automated oscillometric device sequentially, first after the subject is in supine position for at least 3 minutes, then in seated position for at least 3 minutes, and then at 1 minute and at 3 minutes after standing. Changes in blood pressure will be calculated using the minimum standing measurement minus the seated measurement and minus the supine measurement, respectively. A drop of 20 mmHg of systolic blood pressure or a drop of 10 mmHg of diastolic blood pressure from lying to standing or from sitting to standing is considered clinically significant.

The investigator will review the results of vital signs and evaluate and document whether the finding is clinically significant or not. Any clinically significant finding will be reported as medical history (if reported at screening) or as adverse events (if reported during the treatment).

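### SAP 10.4.1 plans percentage change from baseline for signed postural blood-pressure differences, so those percentage columns cannot be interpreted

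*SAP*

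**What the plan says.** SAP 10.4 derives the postural variables at each visit, for systolic and diastolic pressure, as "the minimum standing measurement minus the seated measurement and the minimum standing measurement minus the supine measurement". The denominator of any percentage change is fixed in the same section: "Baseline for all vital signs analyses will be the values obtained at the last assessment prior to the first dose of IMP".

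SAP 10.4.1 then plans: "Mean change and mean percentage (%) change from baseline to visit 3 and to end-of-treatment will be presented for each vital signs variable". A parenthesis brings in the postural variables by name ("including change from sitting to standing and from supine" to standing). A second sentence asks for descriptive statistics of observed values and of "change from baseline (both absolute change and relative change) to visit 3 and at end-of-treatment for each vital signs variable", with the same parenthesis. The postural differences are therefore covered by both requests. Neither section says what to do when the baseline is zero or when baselines differ in sign between women.

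Other planned output bears on the same risk:

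- SAP 10.4.2 counts women with markedly abnormal values as defined in Appendix 1. Table 2 there includes positional drops of 20 mmHg systolic and 10 mmHg diastolic.
- SAP 10.4.3 lists all values, including the positional changes, with flags.
- Protocol 7.4.7 treats as clinically significant "A drop of 20 mmHg of systolic blood pressure or a drop of 10 mmHg of diastolic blood pressure from lying to standing", and applies the same limits from sitting to standing.

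**The concern.** A percentage change is meaningful when the baseline is well away from zero and has the same sign in everyone. Raw blood pressure and pulse meet that condition. A difference between two positions in the same woman need not.

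At a zero baseline the percentage does not exist. Near zero it becomes very large for an ordinary change in mmHg. For a woman whose pressure falls on standing (negative baseline), a larger fall at visit 3 prints as a positive percentage. For a woman whose pressure rises on standing (positive baseline), the same worsening prints as a negative percentage. An arm mean over both kinds of women mixes signs for the same event and is driven by the few baselines nearest zero.

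The variable matters because Protocol 1.3 names orthostatic hypotension as a risk, at 1–10% with the oral tablets. A reader who turns to the percentage column could take the wrong direction from it.

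**Working it through.** The documents state no figure on this point, so there is none to reproduce.

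**1. Formula and examples.** The SAP gives no formula, so the usual one is used: percentage change = 100 × (visit − baseline) / baseline, where both terms are minimum standing minus seated (or supine).

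- −1 to −11 mmHg: 100 × (−10)/(−1) = +1000%
- +2 to −8 mmHg: 100 × (−10)/(+2) = −500%
- −4 to −16 mmHg: 100 × (−12)/(−4) = +300%
- +4 to −8 mmHg: 100 × (−12)/(+4) = −300%
- −10 to −22 mmHg: 100 × (−12)/(−10) = +120%
- 0 to −12 mmHg: division by zero, undefined

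The first two lines are the same 10 mmHg worsening. The last four are the same 12 mmHg worsening.

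**2. What the documents say about baselines.** They give no distribution. Protocol 4.1.2 excludes women with "History of orthostatic hypotension or recurrent syncope" and those with "Any clinically significant abnormal findings from vital signs, blood tests of haematology and clinical chemistry at screening". With the 20/10 mmHg limits of Protocol 7.4.7, this makes large negative baselines unlikely, but it does not fix the mean or the spread.

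**3. Share of zero baselines (assumed distributions).** Take whole-mmHg values, normal, with mean μ of 0, −3, −6 or −10 and SD σ of 5, 8 or 10. Then P(baseline = 0) = Φ((0.5 − μ)/σ) − Φ((−0.5 − μ)/σ).

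- Highest (μ = 0, σ = 5): Φ(0.1) − Φ(−0.1) = 0.0797. Of 72 planned women: 72 × 0.0797 = 5.7. P(at least one) = 1 − (1 − 0.0797)^72 = 99.7%.
- Lowest (μ = −10, σ = 5): Φ(2.1) − Φ(1.9) = 0.0108. Of 72: 72 × 0.0108 = 0.8. P(at least one) is about 54%.

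The share of positive baselines, 1 − Φ((0.5 − μ)/σ), runs from about 2% (μ = −10, σ = 5) to 48% (μ = 0, σ = 8 or 10).

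**4. Behaviour of the arm mean (simulation).** Further assumptions: 36 women per arm (72 at the 1:1 ratio reported in the SAP), a true 5 mmHg worsening, and a correlation of 0.5 between baseline and visit. There were 5,000 repetitions, and women with a zero baseline were left out of the percentage.

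| Baseline mean, SD (mmHg) | Mean % change, 95% range | Share of means above 0 | Mean absolute change, 95% range (mmHg) |
|---|---|---|---|
| 0, 8 | −166% to +62% | 19% | −7.5 to −2.4 |
| −3, 8 | −148% to +102% | 36% | −7.6 to −2.4 |
| −6, 8 | −108% to +134% | 58% | −7.6 to −2.3 |
| −10, 5 | +7% to +144% | 98% | −6.6 to −3.4 |

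Over all the assumed means and SDs the absolute change centres on about −5 mmHg, and its 95% range stays below zero throughout (at its widest about −8.3 to −1.7 mmHg, at SD 10). As a contrast, the percentage change in raw systolic pressure (assumed mean 115, SD 12) has a 95% range of −7.2% to −0.4%. The problem therefore lies in the signed differences and not in percentage change for vital signs generally.

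**5. Overlap with the markedly abnormal counts.** SAP 10.4.2 is limited to women with normal baselines, and the Appendix 1 footnote requires both the criterion value and the stated change from baseline. Read literally for the positional criterion, a woman going from −5 to −22 mmHg systolic passes the 20 mmHg limit but has changed by 22 − 5 = 17 mmHg. That is less than the required 20, so she is not counted. For diastolic pressure, a 10 mmHg positional drop must come with a decrease of at least 15 mmHg.

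**The case against.** The best defence is that little depends on these columns. They are descriptive safety summaries with no test or decision attached. SAP 10.4.1 already plans the absolute change and the observed values for the same variables, with n, mean, SD, median, minimum and maximum. SAP 10.4.2, SAP 10.4.3 and Appendix 1 add counts and flagged listings on the 20/10 mmHg drops. All of this stands, and it limits the point to redundant columns. The counts overlap only partly with a plain by-visit count, for the reasons in step 5 of the working.

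A second defence is that the size is assumed. This also stands. The variable uses the lower of two standing readings, which pulls it downward. With mean −10 and SD 5 only about 1% of baselines are zero and about 2% are positive. Even then a larger drop prints as a positive percentage, and a zero baseline remains possible with no rule to handle it.

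A programmer might divide by the absolute value of the baseline. That would repair the sign (−1 to −11 becomes −1000%, and +2 to −8 stays −500%). It would not repair the zero baseline or the very large values near zero, and the SAP does not specify it.

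A reader might also infer that visit 3 was scheduled to detect orthostatic hypotension. Its timing, 1–5 days after randomisation, fits that, but no section gives it as the purpose. Endocrine and drug-concentration samples are taken at the same visit.

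**Conclusion.** The concern holds for the percentage and relative-change columns of the sitting-to-standing and supine-to-standing differences, systolic and diastolic. The defect follows from the SAP's own definitions and needs no distributional assumption: zero baselines have no percentage, and the sign of the percentage depends on the sign of the baseline.

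How often this would occur does rest on assumptions. Over the range used, 1.1% to 8.0% of baselines per variable are exactly zero. In several scenarios the sign of the arm mean is close to arbitrary despite a true worsening. The count of 0.8 to 5.7 women uses the planned 72.

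A reader might conclude that the whole orthostatic table is meaningless, or that orthostatic effects will go unreported. The documents do not support that, because the mmHg summaries beside the percentages are valid. Nor do they establish that baseline differences centre on zero, or that women with a zero baseline would be dropped; the SAP is silent on both. Percentage changes for raw blood pressure and pulse are not in question. Severity: minor.

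**What to change.** In SAP 10.4.1, state that percentage and relative change are not presented for the sitting-to-standing and supine-to-standing differences. Keep the absolute change in mmHg and the observed values already planned for them.

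Optionally, add a count by visit (visit 3 and end-of-treatment) of women who meet the 20/10 mmHg positional drop. The thresholds already stand in Protocol 7.4.7 and SAP Appendix 1 Table 2, so no new clinical limit is introduced. The count would add to SAP 10.4.2 because it would not be restricted by baseline status or by the additional change-from-baseline condition.

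The cost is one table shell, with no effect on data collection or timing. Protocol 9.8 asks for vital signs and their changes to be handled like the laboratory variables and does not request percentage change, so the deletion does not conflict with the protocol.

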10.4.2 Markedly Abnormal Changes

Summary tables will be prepared displaying the number and percentage of subjects with normal baselines who had one or more pre-specified markedly abnormal treatment-emergent values, according to the definition in Appendix 1.

10.4.3 Data Listings

All vital signs values (including change from sitting to standing and from supine to standing as described above) will be listed by subject number and time point. Markedly abnormal values and clinically significant changes or values will be flagged.

10.5 Physical and gynaecological examinations

Physical and gynaecological examinations are planned at baseline and at end-of-treatment. At the physical examination a number of body systems will be assessed, and at gynaecological examination a number of categories will be assessed. Each resulting in a result of normal, not clinically significant abnormal, or clinically significant abnormal. If multiple examinations are performed after first dose of IMP, then at worst case approach will be used for reporting, such that if any post baseline examination are judged as clinically significant abnormal, this result will be used as the end-of treatment value, and only if all post baseline examinations are judged as normal the end-of-treatment value will be normal.

10.5.1 Summary Statistics

Shift tables summarising the number (%) of subjects that shifted between all combinations of baseline and end-of-treatment values for each body system examined at the physical examination and each category examined at the gynaecological examination will be produced. The number of subjects with baseline values will be used as denominator when percentages are calculated (e.g. the percentage of subjects going from normal to not clinically significant abnormal will be using the number of subjects being normal at baseline as denominator).

10.5.2 Data listings

All subjects with any abnormalities at any visit will be listed with all physical and gynaecological examination evaluations.

10.6 TVU

TVU is planned at baseline and at end-of-treatment. The overall interpretation of TVU results in a result of normal, not clinically significant abnormal, or clinically significant abnormal. If multiple examinations are performed after first dose of IMP, then a worst case approach will be used for reporting, such that if any post baseline examination are judged as clinical significant abnormal, this result will be used as the end-of treatment value, and only if all post baseline examinations are judged as normal the end-of-treatment value will be normal.

